8.1.2. Individual Patient Stopping Rules

If any of the following events occur in an individual patient, administration of study drug to the patient should be interrupted until a review of the accumulated safety data is undertaken by the DMC.

- Any event that fulfills criteria for a Study Stopping Rule (per [Section 8.1.1](#)), unless due to obvious alternative etiology
- Any event that, in the opinion of the Investigator, Medical Monitor, DMC, or Sponsor, contraindicates further dosing

After such a review, the DMC may recommend the patient resume dosing, including consideration for any prophylactic interventions (eg, as per [Section 6.1.3](#)); reduce their dose (as per [Section 6.1.4.1](#)), or discontinue dosing.

8.2. Early Withdrawal of Patients from the Study

In accordance with applicable regulations, a patient has the right to withdraw from the study, at any time and for any reason, without prejudice to future medical care.

Patients may be withdrawn from the study for the occurrence of any of the following reasons:

- Patient request/informed consent withdrawn due to an AE
- Patient request/informed consent withdrawn due to reasons other than an AE
- Patient becomes pregnant
- Adverse event (whether or not related to the study drug) that precludes further participation in the study in the judgment of the Investigator and/or Sponsor
- Protocol noncompliance in the judgment of the Investigator and/or Sponsor
- Lost to follow-up
- The Investigator or Sponsor considers that it is in the patient's best interest for the patient not to continue participation in the study
- Administrative decision by the Investigator or Sponsor.

Patients who withdraw from the study will not be replaced.

Patients are free to withdraw from the study at any time without providing reason(s) for withdrawal and without prejudice to further treatment. The reason(s) for withdrawal will be documented in the eCRF. If a patient withdraws consent, all samples obtained will be retained for analysis unless the patient confirms that he or she wishes the samples to be discarded.

Patients who withdraw from the study prior to W32 will be requested to undergo the ETV procedures within 7 days of the withdrawal, and all patients who withdraw from the study prematurely will be requested to return for the SFU Visit 9 weeks (to perform W40 visit procedures) after receipt of their last dose of the study drug as per [Table 4](#). Patients withdrawing from the study treatment will be encouraged to complete the same final evaluations as patients completing the study according to this protocol, particularly safety evaluations. The primary reason for withdrawal will be identified and recorded on the appropriate eCRF, along with the date of withdrawal.

Reasonable efforts will be made to contact patients who are lost to follow-up. These efforts must be documented in the patient's file.

8.3. Termination or Suspension of the Study

The Sponsor has the right to terminate the study at any time if judged necessary for safety, regulatory, or other reasons consistent with applicable laws, regulations, and Good Clinical Practice (GCP). In this event, the Investigator(s) will be informed of the reason for study termination. Should this occur, all data available will also be recorded in the eCRFs. The Investigator should notify the relevant Institutional Review Boards (IRBs)/Independent Ethics Committees (IECs) in writing of the study's completion or early discontinuation.

9. ADVERSE EVENTS

9.1. Adverse Event Reporting

9.1.1. Definition of an Adverse Event

An AE is defined as any untoward medical occurrence in a clinical study patient administered a medicinal product, which does not necessarily have a causal relationship with this treatment. An AE can therefore be any unfavorable and unintended sign (including an abnormal laboratory finding), symptom, or disease temporally associated with the use of a medicinal (investigational) product, whether or not it is related to the medicinal (investigational) product. This includes an exacerbation of pre-existing conditions or events, intercurrent illnesses, drug interaction or the significant worsening of the indication under investigation that is not recorded elsewhere in the eCRF under specific efficacy assessments. Anticipated fluctuations of pre-existing conditions, including the disease under study, that do not represent a clinically significant exacerbation or worsening need not be considered AEs.

It is the responsibility of the Investigator to document all AEs that occur during the study. Adverse events will be elicited by asking the patient a nonleading question, for example, “Have you experienced any new or changed symptoms since we last asked/since your last visit?” Adverse events should be reported on the appropriate page of the eCRF.

9.1.2. Assessment of Severity

Severity of AEs will be graded according to National Cancer Institute Common Terminology Criteria for Adverse Events (NCI-CTCAE) Version 4.03. If there is a change in severity of an AE, it must be recorded as a separate event.

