- (3: exploratory) by comparing the last response on test treatment between treatments via a crossover design analysis, ie, W16 for patients allocated to the randomized treatment sequence KZR-616 followed by placebo and W32 for patients allocated to the randomized treatment sequence placebo followed by KZR-616, combined, versus W16 for patients allocated to the randomized treatment sequence placebo followed by KZR-616 and W32 for patients allocated to the randomized treatment sequence KZR-616 followed by placebo, combined.

The rationale for this priority order is as follows. The usual crossover analysis for this design is prespecified as exploratory since it is unknown whether that analysis would be confounded by carryover effect. In order to maximize the precision for assessment of KZR-616 effect, it is assessed primarily via all patients' Baseline versus post-Baseline KZR-616 assessment and secondarily by the Treatment Period 1 between-treatment comparison. Summary statistics, including 95% confidence intervals, will be provided for each treatment for each of the 3 types of analysis. Within-patient changes will be analyzed via paired t-tests and corroborated by signed rank tests. Between-patient differences will be analyzed via analysis of covariance, with Baseline as a covariate. The crossover analysis will be via a mixed model repeated measures analysis. Normality will be assessed graphically and via the Shapiro-Wilk statistic. If substantial departure from normality is observed, transformations, eg, natural log and rank, will be explored. P values will be 2-sided with the type 1 error level at 0.05.

Binary endpoints will be summarized by counts and percent and 95% confidence intervals via Clopper-Pearson method. Additional analyses will be specified in the Statistical Analysis Plan (SAP).

Safety Analysis

The safety analysis set will be used for all presentations of safety endpoints. No statistical testing will be used to compare treatment arms for different safety endpoints. Safety data will be summarized descriptively for each test treatment. All AEs will be coded using the current version of the Medical Dictionary for Regulatory Activities (MedDRA). Treatment emergent AEs will be presented within summary presentations by MedDRA system organ class and preferred term, cohort, and treatment arm.

Pharmacokinetic and Pharmacodynamic Analyses

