2.2.2. Safety Endpoints

Safety endpoints are:

- Incidence, nature, and severity of AEs
- Incidence, nature, and severity of SAEs
- Incidence and severity of infection-related AEs and SAEs
- Incidence and severity of AEs with onset within 24 hours from the start of dosing with any study drug
- Incidence of AEs leading to study drug discontinuation
- Changes in standard laboratory parameters, vital signs, and ECGs.

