8.1. Individual and Study Stopping Rules for Safety

8.1.1. Study Stopping Rules

If any of the following events occur, the accumulated safety data will be reviewed by the DMC.

- Death in any patient, unless the cause of death is due to obvious alternative etiology
- Any unexpected or life-threatening SAE, unless due to obvious alternative etiology
- Any event of TMA, thrombotic thrombocytopenic purpura (TTP), or hemolytic uremic syndrome (HUS)
- Three or more of the same Grade 3 or higher AE (judged by the Investigator, Medical Monitor, or Sponsor's representative), including ISRs, unless due to obvious alternative etiology
- Any event which, in the opinion of the Investigator, Medical Monitor, DMC, or Sponsor, contraindicates further dosing of additional patients.

Based on the review, the DMC will have the ability to recommend the study be continued as is, continued with modification, or discontinued. Modifications could include eg, implementation of additional monitoring measures or a dose reduction of KZR-616.

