9.1.6. Documentation and Reporting of Adverse Events

Adverse events (including SAEs) should be reported and documented in accordance with the procedures outlined below. All AEs occurring during the study must be documented on the relevant eCRF pages. The following data should be documented for each AE:

- Diagnosed or description of the symptom if diagnosis is not established
- Classification of 'serious' or 'not serious'

- Classification as AESI (yes or no)
- Severity
- Date of first occurrence and date of resolution (if applicable)
- Action taken with study drug
- Causal relationship with study drug
- Outcome of event (unknown, recovered, not yet recovered, recovered with sequelae, death [with date and cause reported]).

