10.4. Safety Analysis

The safety analysis set will be used for all presentations of safety endpoints. No statistical testing will be used to compare treatment groups for different safety endpoints. Safety data will be summarized descriptively for each test treatment. All AEs will be coded using the current version of the MedDRA. Treatment emergent AEs will be presented within summary presentations, by MedDRA system organ class, preferred term, and treatment group.

Additional analyses will be specified in the SAP.

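### Section 9.1.2 splits an AE at every grade change, and no rule links the records or assigns them to a treatment period, so an AE that began before W16 may be tabulated under the other treatment

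*Combined protocol and SAP*

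**What the plan says.** On recording, Section 9.1.2 requires: "If there is a change in severity of an AE, it must be recorded as a separate event". It does not distinguish worsening from improvement. Section 9.1.6 lists what is documented for each AE, including "Date of first occurrence and date of resolution (if applicable". It does not say whether a record opened by a grade change keeps the original onset date or takes the date of the change.

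On analysis, Section 10.4 says "Safety data will be summarized descriptively for each test treatment", and Section 10.2 bases all summaries on the treatment actually received. The table layout differs between two places. Section 10.4 has "Treatment emergent AEs will be presented within summary presentations, by MedDRA system organ class, preferred term, and treatment group"; the synopsis has "Treatment emergent AEs will be presented within summary presentations by MedDRA system organ class and preferred term, cohort, and treatment arm".

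The safety endpoints in Section 2.2.2 include "Incidence, nature, and severity of AEs" and "Incidence and severity of AEs with onset within 24 hours from the start of dosing with any study drug". Incidence is not defined as patients with at least one event or as number of events. A treatment-emergent AE is not defined, and no rule assigns an AE to a treatment period. Section 10.4 leaves further analyses to the SAP; the combined document supplied has no SAP text that covers this.

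On design, Table 1 in Section 6.1 puts the last Period 1 dose at W15 and the first Period 2 dose at W16, so the only gap is the ordinary weekly interval.

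**The concern.** In a parallel-group trial, splitting an AE by grade mostly affects event counts, because every fragment stays with the same treatment. Here the treatment changes at W16, and a fragment opened after that dose falls in the other treatment's period.

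Take an Arm A patient whose AE began on KZR-616 and eases from Grade 2 to Grade 1 after the first placebo dose. Under Section 9.1.2 the easing is a separate event, and it happens during placebo. Section 9.1.3 treats improvement after withdrawal as positive dechallenge, which points back to KZR-616. The same observation may thus support a causal link to KZR-616 and appear as a record in the placebo column. The mirror case is an Arm B patient whose placebo-period AE changes grade after the first KZR-616 dose.

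The endpoint on onset within 24 hours of dosing is exposed too: a grade change inside that window may be read as an onset although the AE began earlier. With about 12 patients per arm, one or two such records are visible in a table of percentages.

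**Working it through.** The plan states no figure on this point, so there is none to reproduce.

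**Inputs**
- About 12 patients per arm (synopsis, number of arms). If all of about 24 patients receive both treatments, each treatment column has denominator 24.
- Records per AE: 1 + number of grade changes (from Section 9.1.2).
- q, the share of Arm A patients with an AE still open at W16, and r, the probability that its grade then changes. Neither is in the documents. Assumed ranges: q = 0.10 to 0.50, r = 0.25 to 1.0.

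**Step 1: within one treatment.** An AE with 1, 2 or 3 grade changes gives 2, 3 or 4 records. A count of events rises accordingly. A count of patients with at least one event of that preferred term does not change.

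**Step 2: across W16, per patient.** Suppose the new record carries the date of change and tables assign it by that date. Each Arm A patient with such a record, and no other placebo-period record of the term, adds 1/24 = 4.2 points to placebo incidence (1/12 = 8.3 points within Arm A Period 2 alone). Two such patients move 2/24 (8.3%) to 4/24 (16.7%).

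**Step 3: how many patients.** Expected number = 12 × q × r. Added placebo incidence = 12 × q × r / 24. Chance of at least one = 1 − (1 − q × r)^12.

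| q | r | Expected patients | Added points | Chance of at least one |
|---|---|---|---|---|
| 0.10 | 0.25 | 0.3 | 1.25 | 26% |
| 0.25 | 0.50 | 1.5 | 6.25 | 80% |
| 0.50 | 1.0 | 6.0 | 25 | over 99.9% |

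Section 1.5 calls the commonest AEs, injection site reactions, transient and generally mild. To spill over, one must still be open a week after the W15 dose (Day 106 to Day 113) and then change grade rather than resolve. That favours the top of the table.

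**Step 4: direction.** Let a be the number of Arm A patients and b the number of Arm B patients with a spill-over record that counts. The KZR-616 minus placebo difference moves by (b − a)/24. With a = 2 and b = 0 it falls by 8.3 points; with a = 0 and b = 2 it rises by 8.3 points; with a = b it is unchanged.

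**Step 5: Section 8.1.1.** The DMC review criterion reads "Three or more of the same Grade 3 or higher AE" and does not say whether it counts patients, AEs or records. One patient whose AE goes Grade 3, 4, 3 has three records of Grade 3 or higher. Three moves between Grades 2 and 3 (2-3-2-3 or 3-2-3-2) give only two.

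**The case against.** The strongest reply is that Section 9.1.2 governs recording, not counting. No section says that tables count records. If incidence means patients with at least one event, several records of one AE within one treatment count once. This stands, and it limits the multiple-counting part to event counts.

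The second reply is that misattribution needs two things the protocol does not state: that the new record carries the date of change, and that AEs are assigned to a treatment by record date. The first-occurrence wording in Section 9.1.6 can be read as preserving the original onset. This also stands. A reader might infer that every grade change after W16 becomes a new-onset event of the other treatment. The text permits that outcome but does not prescribe it.

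Third, safety is descriptive without testing, AE duration is not a listed endpoint, and the SAP may settle the rules. This lowers the stakes but does not remove the point. The sentence in Section 9.1.2 is mandatory and acts at data capture. If the eCRF does not tie the records of one AE together, an analyst must later guess which belong together.

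Fourth, the Section 8.1.1 criterion involves judgement by the investigator, Medical Monitor or sponsor's representative, exempts obvious alternative causes, and leads to DMC review rather than an automatic stop. A reader might infer that duplicate records would by themselves trip it. The documents do not support that; only the counting unit is open.

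**Conclusion.** The point holds as a risk that the protocol creates and does not control. A mandatory splitting rule that includes improvement, a switch without washout, summaries by treatment received and an onset-based endpoint are combined with no linking or attribution rule. Event counts may be multiplied, and an AE that began before W16 may appear under the other treatment or as an onset soon after dosing.

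The firm figure is conditional: 4.2 points of placebo incidence for each Arm A patient with a spill-over record and no other placebo-period record of the term, assuming about 24 patients reach both treatments. The total of 1.25 to 25 points rests entirely on assumed q and r, and the low end is more plausible for injection site reactions.

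A reader might infer that the KZR-616 versus placebo contrast must shrink. That is not shown: Arm B spill-over works the other way, and neither count is known. The primary efficacy analysis is untouched. The change should be made, because it is cheap before data collection and hard to repair afterwards.

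**What to change.** 1. Change Section 9.1.2 so that a grade change is a dated entry within, or linked to, one AE, which keeps its date of first occurrence and its maximum grade. Linked separate records would serve equally well, provided the link is captured on the eCRF.
2. State in Section 10.4 and the SAP that an AE is attributed to the treatment at first occurrence, and counts as newly treatment-emergent in Period 2 only if its grade rises after the first W16 dose. Base the 24-hour endpoint on the same date of first occurrence.
3. Define incidence as patients or events, and reconcile the table grouping in the synopsis with that in Section 10.4.
4. State whether the Section 8.1.1 criterion counts patients, AEs or records, and reconcile it with Section 9.1.2. Which unit to use is for those responsible for that rule.

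The cost is a small eCRF change and added SAP wording. The dated grade history is kept, so no safety information is lost.

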9.1.3. Assessment of Causality

Adverse events will be deemed related to study medication unless clearly unrelated to study medication.

The Investigator will assess the causal relationship between KZR-616 (or placebo) and AE. One of the following categories should be selected based on medical judgment, considering the definitions below and all contributing factors.

Related	A clinical event, including laboratory test abnormality, occurs in a plausible time relationship to treatment administration and which concurrent disease or other drugs or chemicals cannot explain. The response to withdrawal of the treatment (dechallenge ^a) should be clinically plausible. The event must be definitive pharmacologically or phenomenologically, using a satisfactory rechallenge ^b procedure if necessary.
Unrelated	A clinical event, including laboratory test abnormality, with little or no temporal relationship with treatment administration. May have negative dechallenge and rechallenge information. Typically explained by extraneous factors (eg, concomitant disease, environmental factors, or other drugs or chemicals).

- a Dechallenge: Upon discontinuation of a drug suspected of causing an AE, the symptoms of the AE disappear partially or completely, within a reasonable time from drug discontinuation, (positive dechallenge), or the symptoms continue despite withdrawal of the drug (negative dechallenge). Note that there are exceptions when an AE does not disappear upon discontinuation of the drug, yet drug-relatedness clearly exists (for example, as in bone marrow suppression, fixed drug eruptions, or tardive dyskinesia).
- b Rechallenge: Upon re-administration of a drug suspected of causing an AE in a specific patient in the past, the AE recurs upon exposure (positive rechallenge), or the AE does not recur, (negative rechallenge).

9.1.4. Action Taken

The Investigator will describe the action taken with study drug in the appropriate section of the eCRF, as follows:

- None
- Study drug stopped
- Study drug temporarily interrupted
- Study drug dose reduced (only permissible with Medical Monitor confirmation in writing)
- Other, specify.

9.1.5. Follow-up on Adverse Events

Adverse events are intended to be collected according to the procedures outlined above from the time of informed consent and to continue for 30 days following the last dose, or the End of Study Visit, whichever occurs later.

All Investigators should follow up with patients with AEs until the event is resolved or until, in the opinion of the Investigator, the event is stabilized or determined to be chronic. Details of AE resolution must be documented in the eCRF.

9.1.6. Documentation and Reporting of Adverse Events

Adverse events (including SAEs) should be reported and documented in accordance with the procedures outlined below. All AEs occurring during the study must be documented on the relevant eCRF pages. The following data should be documented for each AE:

- Diagnosed or description of the symptom if diagnosis is not established
- Classification of 'serious' or 'not serious'

- Classification as AESI (yes or no)
- Severity
- Date of first occurrence and date of resolution (if applicable)
- Action taken with study drug
- Causal relationship with study drug
- Outcome of event (unknown, recovered, not yet recovered, recovered with sequelae, death [with date and cause reported]).

9.2. Serious Adverse Events

9.2.1. Serious Adverse Event Definition

An SAE is any untoward medical occurrence or affect that, at any dose,

- Results in death
- Is life-threatening (an AE is life-threatening if the patient was at immediate risk of death from the event as it occurred, ie, it does not include a reaction that might have caused death if it had occurred in a more serious form)
- Requires or prolongs inpatient hospitalization. (Complications occurring during hospitalization are AEs and are SAEs if they cause prolongation of the current hospitalization. Hospitalization for elective treatment of a pre-existing nonworsening condition is not, however, considered an AE. The details of such hospitalizations must be recorded on the medical history or physical examination page of the eCRF)
- Results in persistent or significant disability/incapacity. (An AE is incapacitating or disabling if it results in a substantial and/or permanent disruption of the patient's ability to carry out normal life functions)
- Results in a congenital anomaly/birth defect.

In addition, medical and scientific judgement is required to decide if prompt notification is required in situations other than those defined for SAEs above. This may include any event that the Investigator regards as serious that did not strictly meet the criteria above but may have jeopardized the patient or required intervention to prevent one of the outcomes listed above, or that would suggest any significant hazard, contraindication, side effect, or precaution that may be associated with the use of the investigational product.

